**Figure 1 Flow of data for study**

### 7.3 Statistics

Details of the planned analyses will be described in the Statistical Analysis Plan (SAP), providing a detailed discussion of the analyses outlined below. Any deviations from the planned analyses will be described and justified in the final clinical study report. The SAP will be finalized before data base release and the subsequent unblinding.

All study data will be listed, and all endpoint data will be tabulated. All categorical data will be tabulated by frequency and percentage while all continuous data will be tabulated by arithmetic mean, standard deviation, and range. Data used for log-transformed analyses will also be tabulated by geometric mean and coefficient of variation. This will be relevant for the immunogenicity endpoints. Exposure to vaccinations and compliance with the vaccination schedule will be tabulated and listed. All statistical analyses will be adjusted by site, as randomisation is stratified.

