## 7.9 Analysis of immunogenicity (secondary endpoints)

The following secondary immunogenicity endpoints will be evaluated by standard tabulation by vaccination group and relevant time-point(s):

Based on samples collected in the mother (MIG analysis set):

- Concentrations of IgG antibodies specific to the 4 AlpN proteins in maternal blood, pre-dosing, 4 weeks after each vaccination dose and at delivery
- Relative to baseline (pre-dose) concentrations of IgG antibodies specific to the 4 AlpN proteins in maternal blood, pre-dosing, 4 weeks after each vaccination dose and at delivery
- The proportions of mothers who achieve a concentration of IgG specific to the 4 AlpN proteins above 0.1, 0.2, 0.5, 1, 2, 4 and 8 µg/mL at delivery
- The subject level ratios of antibody concentrations between maternal and cord blood at delivery

Based on samples collected in the baby (BIG analysis set):

- Concentrations of IgG antibodies specific to the AlpN proteins in infant blood of each baby at 1 month and 3 months of age:
- The proportions of babies who achieve a concentration of IgG specific to the AlpN proteins above 0.1, 0.2, 0.5, 1, 2, 4 and 8 µg/mL at 1 month and 3 months after birth will be calculated

For treatment groups 1 to 4, in a joint analysis, the maternal IgG concentrations from pre-dosing to delivery will be analysed using a log-normal model with repeated measurements within subject, vaccination group and visit as factors. Possibly allowing for changing variance across visits and visit times group interaction. In this way the ratio of GMCs (GMCR) comparing vaccination groups can be derived.

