## 2.5 Randomization

In accordance with Table 1 above, patients are randomized into groups 1 to 5 using the allocation ratio 2:2:2:2:1. This is achieved by stratifying randomization on site (10 sites) and, within site, using blocking of size 9 with each block containing two occurrences of a given active group (1 to 4) and one occurrence of placebo (group 5) in random order. The assignment of group to any new eligible patient occurs through the eCRF in such a way that blinded staff will have access to the randomization date and number only. The randomization list is prepared and uploaded to the eCRF system by a statistician who remains in an unblinded role throughout the blinded part of the study.

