$$H_0: P_{\text{cut } c, \text{ group } k, \text{ antigen } w} < P_{\text{cut } c, \text{ group } 1, \text{ antigen } w} - 0.15$$
$$k = 2, 3, 4; w = 1, 2, 3, 4; c = 0.1, 0.2, 0.5, 1, 2, 4, 8$$

$P_{\text{cut } c, \text{ group } k, \text{ antigen } w}$  is thus the proportion of subjects with antibody levels above cut-point  $c$ , for vaccination group  $k$  when considering the IgG concentration specific to antigen  $w$ .

The statistical alternative hypothesis is thus:

$$H_1: P_{\text{cut } c, \text{ group } k, \text{ antigen } w} \geq P_{\text{cut } c, \text{ group } 1, \text{ antigen } w} - 0.15$$

If  $H_0$  is rejected this indicates non-inferiority for one specific cut point and antigen.

The evaluation will be done by calculation of the unadjusted risk difference:

$$(P_{c, \text{ group } k, w} - P_{c, \text{ group } 1, w})$$

with a two-sided 90% CI, corresponding to a one-sided test at the 5% significance level. The CI's will be approximative Newcombe-Wilson intervals. The  $H_0$  is rejected if the CI is fully above the -15% point limit, and this therefore corresponds to a one-sided test at a 5% level.

The derivation of the unadjusted risk differences ( $P_{c, \text{ group } k, w} - P_{c, \text{ group } j, w}$ ), with corresponding two-sided 90% CIs, will be derived for all pairs  $1 \leq k, j \leq 4$  and all antigens  $1 \leq w \leq 4$ .

For the observed IgG concentrations, the comparison will be done with the same grouping, but using geometric mean concentrations. Here the  $H_0$  can be expressed as:

$$H_0: \text{GMC}_{\text{group } k, \text{ antigen } w} < 2/3 * \text{GMC}_{\text{group } 1, \text{ antigen } w}$$
$$k = 2, 3, 4; w = 1, 2, 3, 4$$

The evaluation will be done by calculation of the GMCR (GMC ratio) with a two-sided multiplicative 90% CI, again corresponding to a one-sided test at the 5% significance level. The CI's will be based on log-normality. The  $H_0$  is rejected if the CI is fully above the GMCR=2/3 limit and this therefore corresponds to a one-sided test at a 5% level.

The derivation of the GMCRs with corresponding two-sided 90% CIs, will be derived for all pairs  $1 \leq k, j \leq 4$  and all antigens  $1 \leq w \leq 4$ .

As a supplementary analysis, all groups (including placebo) are compared using Analysis of Variance (ANOVA) of the log-transformed values. No adjustment for multiplicity is done.

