For treatment groups 1 to 4, in a joint analysis, the maternal IgG concentrations from pre-dosing to delivery will be analysed using a log-normal model with repeated measurements within subject, vaccination group and visit as factors and a visit \* group interaction.

An unstructured covariance structure will be implemented for repeated measurements. In case of estimation issues, an auto-regressive AR(1) covariance structure will be used instead to model the correlations within-subject. The Satterthwaite approximation will be used to estimate denominator degrees of freedom and adjust standard errors.

Pseudo code related to the implementation of this model:

```
proc mixed data = IgG data;  
  class subject group visit region;  
  model change_log_titre = baseline region group*visit / ddfm=sat;  
  repeated visit / subject=subject type=UN;  
  lsmeans group*visit / diff cl obsmargins;  
run;
```

Here *change\_log\_titre* is the change from baseline in log(titre), *baseline* is the log(titre) at baseline and *visit* is the study Visit (i.e., 3, 5, 7, 8).

Least square mean estimates of change from baseline in log(titre) with 95% confidence intervals (CI) will be presented after applying the inverse transformation at each time-point for each treatment group.

Estimated group differences at Visit 7 and 8 (when vaccination schedule has been completed) between vaccination groups along with associated 95% confidence intervals and p-values will be presented.

Estimated least square means and associated 95% CI of change from baseline in log(titre) will be plotted over time by treatment group.

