#### 4.8 Analysis of weight of infant (exploratory endpoint)

Weight of the infant is not considered an endpoint in the protocol. It is however measured on four occasions and since weight of newborns is generally considered of medical importance weight will be made, comparing the 5 treatment groups (including group 5). The change-from-baseline (birth) in infant weight will be analyzed using a simple random effects model. Pseudo code related to the implementation of this model:

```
proc mixed data = weight data;  
  class subject group visit region;  
  model change_weight = birth_weight region group*visit / ddfm=sat;  
  random intercept / subject=subject;  
  lsmeans group*visit / diff cl obsmargins;run;
```

*Change\_weight* is the change from baseline in weight and *visit* is the study Visit (i.e., 9, 10, 11). Least square mean estimates of change from baseline in weight with 95% confidence intervals (CI) will be presented at each visit for each vaccination group. Estimated group differences at visit 11 between vaccination groups along with associated 95% confidence intervals and p-values will be presented. Estimated least square means and associated 95% CI of change from birth weight will be plotted over time, by vaccination group.

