## 7 Deviations from protocol

- An exploratory analysis of weight of infant over time is added.
- Adverse events in babies are added as secondary safety endpoint(s).
- Central monitoring is described in some detail, but no specific analysis of monitoring data is defined.

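### Protocol 7.3 promises site adjustment in every analysis, but the primary risk difference is unadjusted, the GMC-ratio model does not mention site, and SAP section 7 declares neither

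*SAP*

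**What the plan says.** Protocol 7.3 sets a general rule and gives its reason: "All statistical analyses will be adjusted by site, as randomisation is stratified". SAP 2.5 confirms that randomisation is stratified on ten sites, in blocks of nine at 2:2:2:2:1. The specific sections read differently:

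- **Primary proportions.** SAP 4.5: "The evaluation will be done by calculation of the unadjusted risk difference", with a 90% Newcombe-Wilson interval. Protocol 7.8 says the same.
- **Primary GMC ratio.** Both documents describe a 90% interval and add only "The CI's will be based on log-normality". Neither mentions site. The supplementary ANOVA in SAP 4.5 does not mention it either.
- **Maternal IgG.** Protocol 7.9 describes a "log-normal model with repeated measurements within subject, vaccination group and visit as factors". SAP 4.6 writes it as "model change_log_titre = baseline region group*visit / ddfm=sat".
- **Infant weight.** SAP 4.8: "model change_weight = birth_weight region group*visit / ddfm=sat".

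Region is not defined beside either model; SAP 4.1 suggests South Africa against Europe. SAP section 7 lists three departures, beginning with "An exploratory analysis of weight of infant over time is added". The other two are baby adverse events and central monitoring. None concerns site.

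**The concern.** Three separate matters are involved.

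1. For proportions, 7.3 and 7.8 cannot both be followed. The conflict lies within the protocol, and the SAP repeats the 7.8 side.
2. For the GMC ratio the text is ambiguous rather than contradictory. Read under 7.3, site is in the model. Read beside the unadjusted risk difference, it is out. The two readings give different intervals, and the choice should not remain open once data are unblinded.
3. The modelled analyses replace the stratification factor with a coarser one, without saying so.

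The statistical stake is precision. Blocking within site balances site across groups, so between-site variation largely cancels from the group difference. An analysis that omits site still counts that variation in the standard error. The interval then over-covers and power is lost. The Protocol synopsis says the testing is mainly meant to guide which schedule goes forward, so the width of these intervals matters to that choice.

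**Working it through.** **Plan's own figure.** Protocol 7.13 and SAP 2.3.1 state power above 90% for proportions at 1 µg/mL. Inputs: rate 22/23 = 95.65% in both groups, 60 per group, margin 0.15, unadjusted two-sided 90% Newcombe-Wilson interval. Exact binomial enumeration gives 96.7%. With 54 or 48 evaluable babies per group it gives 94.7% or 92.1%. The claim reproduces without adjustment.

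**GMC ratio, no site effect.** Inputs from the documents: 60 v 60, margin 2/3, one-sided 5%. The log SD is assumed.
- SE = SD × √(2/60) = 0.1826 × SD. Distance to the margin is ln(1.5) = 0.4055.
- At SD 1.0 the noncentrality is 0.4055/0.1826 = 2.221. With 118 df (critical t 1.658), power is 71.3%.
- At SD 1.2, 1.5 and 2.1, power is 57.7, 43.1 and 27.6%.

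**With a site effect.** Let R² be the share of log-titre variance due to site, also assumed. Under exact balance the true SE of the log ratio is SD × √((1−R²) × 2/60), but an interval without site is built on the full SD.
- True one-sided error without site = 1 − Φ(1.645/√(1−R²)). For R² = 5, 10 and 20% this is 4.6, 4.1 and 3.3%. Simulations at SD 1.0 gave 4.4–4.8, 3.9–4.3 and 3.4–3.7%. With site in the model, error stays near 5%.
- Width with site relative to without is about √(1−R²) = 0.975, 0.949 and 0.894. Simulated half-widths at SD 1.0 were 0.2944 v 0.3014, 0.2868 v 0.3009 and 0.2701 v 0.2991, which is about 2, 5 and 10% narrower.
- Power with site at SD 1.0 and R² = 10%: SE = 0.1732, noncentrality 0.4055/0.1732 = 2.341, df = 120 − 11 = 109, power 75.2%. Simulation gave 74.9%.

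Simulated power (%), without → with site, for equal regimens and ten balanced sites with six women per group per site (20,000 runs per cell):

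| log SD | share 0% | 5% | 10% | 20% |
|---|---|---|---|---|
| 1.0 | 71.1 → 71.0 | 71.6 → 73.0 | 72.4 → 74.9 | 74.4 → 79.7 |
| 1.2 | 57.3 → 57.2 | 58.4 → 60.0 | 58.4 → 61.6 | 59.2 → 65.9 |
| 1.5 | 42.9 → 42.9 | 43.4 → 44.9 | 42.7 → 45.6 | 42.9 → 49.7 |
| 2.1 | 27.7 → 27.6 | 27.1 → 28.4 | 26.9 → 29.6 | 26.3 → 32.1 |

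**Unequal sites.** With assumed site sizes from 5 to 50 (total 270), incomplete blocks and SD 1.0, power without → with site is 71.0 → 70.6, 71.4 → 72.3, 72.5 → 74.5 and 74.3 → 78.9% at shares 0, 5, 10 and 20%.

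**Region in place of site.** Same unequal sites, SD 1.0, share 10%, one model across Groups 1–4. If site effects are unrelated to region, power is 73.2% with region and 75.3% with site, and error with region is 4.3%. If the whole share lies between regions, the two are equivalent (75.3 v 75.2%).

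**The case against.** The strongest reply is that little is at risk. The error is on the safe side. SAP 4.5 calls the tests non-confirmatory, expects low power in many of them and intends only descriptive use. The gain depends on assumed inputs and is nil if site is not prognostic. At SDs of 1.5 to 2.1, power is roughly 26 to 50% either way. No regimen choice is shown to change. All of this stands and limits the weight of the point.

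It can also be argued that silence on the GMC ratio means 7.3 applies, since only the risk difference is labelled unadjusted and the SAP presents itself as an elaboration of the protocol. That reading is possible. The loss calculated above arises only on the other reading, and the need for a stated model is the same under both.

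For proportions, protocol and SAP agree on the method, so the SAP departs only from 7.3 and not from 7.8. That is correct, and it is why the protocol sentence itself needs correcting.

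Two technical points also stand. The supplementary ANOVA and the placebo contrasts need the same decision. With unequal sites, site-adjusted ratios need not equal the ratios of the group GMCs reported in SAP 4.5. The separate South Africa and Europe tables in SAP 4.1 do not answer the concern, because they do not adjust the between-group interval.

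**Conclusion.** The concern holds and should be fixed. The inconsistency can be read directly from the documents: 7.3 conflicts with 7.8 and SAP 4.5 for proportions, the GMC-ratio model is unspecified as to site, region stands in for site in the written models, and SAP section 7 is silent. The statistical consequence is modest. If site is prognostic and is omitted, the GMC-ratio interval is conservative. The cost is about 1–2, 3 and 5–7 points of power at site shares of 5, 10 and 20%, and nothing at 0%. The direction rests on blocking within site and additive site effects; the size rests on the assumed SD and site share. The stated power for proportions is unaffected.

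**What to change.** **GMC ratio.** Add to SAP 4.5: *Each GMC ratio is estimated from a linear model of ln cord-blood IgG with group and site, fitted to the two groups being compared; the two-sided 90% CI and the 2/3 margin are unchanged. The ratio without site is a sensitivity analysis.* State in the same place whether site enters the supplementary ANOVA and the placebo contrasts, and note that adjusted ratios may differ from the ratios of the tabulated GMCs.

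Fit pairwise. Pooling Groups 1–4 gains at most 0.4 points of power when SDs are equal. It moves the Group 2 v 1 error to 2.9% if Group 4's SD is 1.5 times the others, and to 6.3% if it is 0.7 times.

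**Proportions.** Keep the unadjusted Newcombe-Wilson interval.

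**Reconciliation.** Amend Protocol 7.3 to state the exception for proportions and the use of region in the SAP 4.6 and 4.8 models. Define region, and list the departures in SAP section 7. Settle this before the unblinded Visit 8 analysis, which reports the primary endpoint.

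**Optional.** A region-stratified interval for proportions could be a sensitivity analysis. Ln maternal Visit 1 IgG could be added for precision, but its missing values must first be reconciled with the no-imputation text.

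**Cost.** No new data and no extra women. Site uses 9 degrees of freedom per ratio: if site is not prognostic, this loses 0.1 point of power with balanced sites and 0.4 with unequal ones (60 v 60). A site with no woman in one of the two groups contributes nothing to that ratio; the unequal-site figures include this. The cost for the 60 v 30 placebo contrasts was not calculated. Under Protocol section 12, the 7.3 amendment needs authority and ethics approval if it is judged substantial.

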The four proteins, Rib, Alp1, AlpC and Alp2/3, are found on most isolates of all serotypes (Ia, Ib, II, III, IV, V, VI, VII, VIII and IX). Antibodies directed against the vaccine were found to recognize nearly 100% of 154 clinical isolates of serotypes Ia, Ib, II, III and V tested for antibody binding. Furthermore, the Rib protein is expressed on most serotype III strains, which cause almost all cases of meningitis, and by all strains of a hyper-virulent type III clone (Baker and Edwards 2003; Brimil et al. 2006; Brochet et al. 2006).

Naturally occurring antibodies against the full-length Rib, Alp1, AlpC and Alp2/3 proteins are found in pregnant and non-pregnant women, probably due to exposure to GBS from colonization or infections such as GBS urinary tract infections, and such antibodies are efficiently transferred to their babies *in-utero*.

Importantly, a correlation between high concentrations of such antibodies directed against the N-terminal domains, in the mothers and their new-borns are associated with a reduced incidence of invasive GBS disease in the new-borns (Larsson, Stålhammar-Carlemalm, and Lindahl 1999).

A case-control study in neonates with invasive GBS disease and relevant controls of neonates born to mothers carrying the same GBS isolates, but not contracting GBS disease, has shown that a preliminary estimate for the predicted threshold for 90% protection against invasive disease is a concentration of IgG specific to the N-terminal domain of the Rib protein of 0.52 µg/ml, and for Alp1 specific IgG: 0.12 µg/ml (Minervax Internal Report MVX012).

For details on the physical, chemical and pharmaceutical properties of the GBS-NN/NN2 vaccine, please refer to the IB.

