## 7.8 Analysis of immunogenicity (primary endpoint)

The primary objective of the study will be assessed using the following endpoints, based on cord blood from subjects in the BIG set:

- A) IgG antibody concentrations specific to each of the four chosen AlpN proteins
- B) Seroprotection as defined by AlpN-specific IgG concentrations being above the following cut points: 0.1, 0.2, 0.5, 1, 2, 4 and 8 µg/mL

The primary immunological endpoints will be defined as the values of the above parameters obtained in cord blood at the time of delivery (anticipated to be approximately 18 weeks from administration of first vaccine dose, taking place at the pregnancy's 22 weeks gestational age).

The endpoints will be compared, as described below, between the 5 intervention groups:

- Group 1: 2 doses GBS-NN/NN2 at 26 & 30 weeks GA  
(1st dose given 3rd trimester; 4 weeks interval)
- Group 2: 2 doses GBS-NN/NN2 at 22 & 26 weeks GA  
(1st dose given 2nd trimester; 4 weeks interval)
- Group 3: 2 doses GBS-NN/NN2 at 22 & 30 weeks GA  
(1st dose given 2nd trimester; 8 weeks interval)
- Group 4: 1 dose GBS-NN/NN2 at 26 weeks GA  
(one dose given 3rd trimester)
- Group 5: Placebo at 22, 26 & 30 weeks GA  
(1st placebo dose given 2nd trimester, 4 weeks interval)

Comparison between groups 1, 2, 3 and 4 will form the main focus, with group 1 as the perceived standard, whereas groups 2 and 3 each represent useful practical alternatives that are expected to perform on a comparable level, and group 4 as representative for a sub-optimal, but still useful vaccination experience.

**Estimand:** The 'treatment-policy (ITT/effectiveness)' estimand is considered for the primary objective. The estimand is based on data collected in all randomized BIG subjects regardless of the mother's possible discontinuation of trial product or treatment adherence.

**Missing data:** imputation is not envisaged, and data will be analysed as collected. In general, the attrition rate is expected to be low.

The comparison will be conducted as a series of non-inferiority tests, for each choice of antigen (4) and cut-point (7) with two margins:

- binary endpoints (seroprotection): 15% points (0.15) on the absolute scale
- for IgG concentrations: here a GMC ratio of 2/3 is considered adequate.

The null hypotheses for each binary endpoint is:

$$H_0: P_{\text{cut } c, \text{ group } k, \text{ antigen } w} < P_{\text{cut } c, \text{ group } 1, \text{ antigen } w} - 0.15$$

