## 1 Introduction

This document describes the planned statistical analyses for the GBS-NN/NN2 Study with the Study ID MVX0004 and is an elaboration on the analysis outlined in protocol version 5.0 dated 14-Apr-2023 [1].

Group B Streptococcus (GBS) is a widely distributed commensal, which can colonize the vagina of pregnant women and on occasion provoke invasive GBS disease like sepsis, pneumonia and meningitis in infants. Global incidence is thought to be about 0.5 per 1000 live births, but with large geographical variation. Neonatal infections will typically occur within the first 3 months. A distinction is conventionally made between EOD ‘type’ (occurrence days 1-6) and LOD (days 7-89). In principle infections could thus be prevented by vaccination of the pregnant mother by which the antibody is passively transferred to the fetus (Brechje de Gier et al. 2019 [2]).

Most women already have a variety of naturally occurring antibodies against GBS antigens. IgG is the most relevant antibody class in terms of immunity. These can be induced by a family of GBS surface proteins, called Alp-proteins. These proteins are anchored in the cell membrane through certain components, one of which is a functionally active N-terminal domain which facilitate invasion of epithelial cells and crossing of the blood-brain barrier. So far, six members of the Alp-proteins have been characterized (Rib, AlpC, Alp1, Alp2, Alp3, Alp4), of which 4, i.e., RibN, Alp1N, Alp2N, and AlpCN, are included in the MinervaX vaccine through 2 fusion proteins, GBS-NN and GBS-NN2, each containing 2 of the N-terminal domains mentioned above. The focus of this protein vaccine study is on the antibody level in the blood of mother and child alike. The risk of a high concentration of the GBS organism in the baby blood is reduced by increasing the concentration of the IgG antibodies which are transferred across the placenta to the infant in utero.

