#### 4.5 Analysis of immunogenicity (primary endpoint)

The primary objective of the study will be assessed using the following endpoints, based on the cord blood from subjects in the BIG set:

- A) IgG antibody concentrations specific to each of the four chosen AlpN proteins.
- B) Proportion of subjects reaching AlpN-specific IgG concentrations at or above the following cut points: 0.1, 0.2, 0.5, 1, 2, 4 and 8 µg/mL.

The primary immunological endpoints will be defined as the values of the above parameters obtained in cord blood at the time of delivery. According to protocol, a missing or invalid cord blood sample can be replaced by a venous infant blood sample, provided this is taken within 72 hours from delivery.

The GMC and corresponding 95% CI for the IgG antibody concentrations will be estimated, by intervention group, assuming a normal distribution on the log-scale, the anti-log transformation will then be applied before presentation. The proportion of subject reaching the IgG antibody concentrations above the prespecified cut points will be reported by intervention group and 95% confidence intervals will be derived using the Wilson method. Additionally, the endpoints will be compared, as described below, between the 5 intervention groups presented in Table 1.

In terms of interpretation, comparison between groups 1, 2, 3 and 4 will form the main focus, with group 1 as the perceived standard, whereas groups 2 and 3 each represent useful practical alternatives that are expected to perform on a comparable level, and group 4 as representative for a sub-optimal, but still useful vaccination experience that would be likely to occur in practice.

**Estimand:** The ‘treatment-policy (ITT/effectiveness)’ estimand is considered for the primary objective. The estimand is based on data collected in all randomized BIG subjects regardless of the mother’s possible discontinuation of trial product or treatment adherence.

**Missing data:** imputation is not envisaged, and data will be analysed as collected.

The comparison will be conducted as a series of non-inferiority tests, for each choice of antigen (4) and cut-point (7) with two margins:

- for IgG concentrations: here a GMC ratio of 2/3 is considered adequate.
- for binary endpoints (proportion of subjects with antibody concentrations over prespecified thresholds): 15% points (0.15) on the absolute scale

The null hypothesis for each binary endpoint is:

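### The primary cord-blood GMC ratio ignores the mother's pre-dose IgG, a modest and avoidable loss of precision; separately, the SAP drops the protocol's placebo comparison of proportions, which the lowest cut-points need

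*SAP*

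**What the plan says.** **Primary analysis.** SAP 4.5 compares Groups 2, 3 and 4 with Group 1 on cord-blood IgG to each of four antigens. For concentrations it says: "The evaluation will be done by calculation of the GMCR (GMC ratio) with a two-sided multiplicative 90% CI". The interval rests on log-normality, and the margin is given as "for IgG concentrations: here a GMC ratio of 2/3 is considered adequate". For proportions it uses an explicitly unadjusted risk difference with a Newcombe-Wilson interval and a margin of "15% points (0.15) on the absolute scale" at all seven cut-points from 0.1 to 8 µg/mL. Neither comparison names a covariate, and nor do the supplementary ANOVA or the sensitivity analyses.

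**Baseline.** Protocol 4.3.2 schedules a maternal immunogenicity sample before the first injection at Visit 1, and SAP 4.4.2 defines it as the IgG baseline. The secondary maternal analysis in SAP 4.6 uses it: "model change_log_titre = baseline region group*visit / ddfm=sat". Protocol 2.3 says that natural antibodies to the full-length Alp proteins occur in pregnant women and that "such antibodies are efficiently transferred to their babies". Protocol 7.3 says every statistical analysis will be adjusted by site because randomisation is stratified; SAP 4.5 does not carry this over.

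**Placebo.** Protocol 7.8 applies the same analysis to Groups 1-4 against Group 5, with superiority p-values, estimated differences and 90% intervals. SAP 4.5 limits pairwise risk differences and GMC ratios to Groups 1-4 and brings placebo in only through an ANOVA of log concentrations. SAP 7 does not list this among the departures from the protocol.

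**The concern.** A baby's cord IgG reflects both the response to vaccine and whatever the mother already had. The second part is measured before treatment. If it predicts cord IgG, leaving it out puts explainable between-woman spread into the residual and widens every primary GMC ratio interval. The study would then be adjusting its secondary maternal analysis for baseline but not its primary cord-blood one.

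The second issue is separate. At a cut-point that most unvaccinated babies already exceed, a 15-point margin may be wider than the whole difference between Group 1 and placebo. Passing the non-inferiority test there would say little about the regimen.

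Both matter because the protocol synopsis says the tests are there to guide the choice of schedule, and Protocol 2.5 says the cord-blood results, with safety, will select the phase III regimen. The low cut-points are not idle: Protocol 2.3 gives a preliminary protective estimate of 0.12 µg/mL for Alp1.

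**Working it through.** **1. The plan's own power figure.** Inputs from SAP 2.3.1 and 4.5: rate 95.65% in both groups at 1 µg/mL, 60 per group, margin 0.15, 90% Newcombe-Wilson interval. Exact enumeration of the 61 × 61 outcomes gives power 96.7%, so the stated figure of above 90% reproduces. The plan states no power for the GMC ratio.

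**2. Power of the GMC ratio test.** From the documents: margin ln(1.5) = 0.405, 60 per arm, and intervals "with a two-sided 90% CI, corresponding to a one-sided test at the 5% significance level". The SD of log cord IgG is not given. A rough guide comes from the phase I rates at 2 and 4 µg/mL, using SD = ln 2 / (z(rate at 2) − z(rate at 4)):

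- Rib: 0.693 / (0.939 − 0.276) = 1.05
- AlpC: 0.693 / (1.360 − 0.641) = 0.96
- Alp1: 0.693 / (1.712 − 1.125) = 1.18
- Alp2: 1.97, poorly determined

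These come from 23 non-pregnant women, so the SD is an assumption, shown from 0.9 to 1.5. The correlation r between maternal baseline and cord log IgG is also an assumption.

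Adjustment multiplies the residual SD by √(1 − r²). At a true ratio of 1, power = Φ( 0.405 / (SD × √(1 − r²) × √(2/60)) − 1.645 ). For SD 1.0 and r = 0: 0.405 / 0.1826 = 2.221; 2.221 − 1.645 = 0.576; power 72%.

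| Assumed log-SD | r = 0 | r = 0.2 | r = 0.3 | r = 0.5 |
|---|---|---|---|---|
| 0.9 | 79.5% | 80.9% | 82.7% | 88.6% |
| 1.0 | 71.8% | 73.3% | 75.3% | 82.1% |
| 1.2 | 58.2% | 59.6% | 61.6% | 68.9% |
| 1.5 | 43.5% | 44.7% | 46.3% | 52.6% |
| Interval width factor √(1 − r²) | 1 | 0.980 | 0.954 | 0.866 |
| Equivalent unadjusted n per arm, 60/(1 − r²) | 60 | 62.5 | 65.9 | 80.0 |

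**3. Which r is plausible?** Suppose natural IgG simply adds to an independent vaccine response (assumed background log-SD 1.2; vaccine GMC 5.3 µg/mL, log-SD 1.0). Simulation then gives r = 0.06, 0.14, 0.21 and 0.33 for background GMCs of 0.1, 0.3, 0.5 and 1 µg/mL. That favours the left of the table. A response that scales with baseline would give a larger r. The documents do not settle which holds.

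**4. Low cut-points.** The Newcombe lower bound is d − √((p_k − l_k)² + (u_1 − p_1)²), with Wilson limits. With Group 1 at 60/60, u_1 − p_1 = 0. At 56/60 the bound is −0.067 − 0.074 = −0.141 (pass); at 55/60 it is −0.083 − 0.078 = −0.161 (fail). The chance that a regimen sitting at the background rate passes is:

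| Assumed background rate | Group 1 at 100% | Group 1 at 95.65% |
|---|---|---|
| 85% | 4% | 19% |
| 90% | 27% | 56% |
| 93% | 59% | 83% |
| 95% | 82% | 94% |
| 98% | 99% | >99% |

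No placebo rate is given. For 93% to exceed a cut-point c, the background GMC must be c × exp(1.476 × SD). With log-SD 0.8-1.5 that is 0.33-0.91 µg/mL at 0.1, 0.65-1.83 at 0.2 and 1.6-4.6 at 0.5. So 0.1, and perhaps 0.2, are the candidates.

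**5. Does baseline adjustment cure step 4?** No. In a simulation with background GMC 0.5 and cut-point 0.1, the difference from Group 1 is −0.101 both unadjusted and adjusted. The two issues need separate remedies.

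**The case against.** An unadjusted GMC ratio is a legitimate choice in a randomised trial, and if r is small the gain is only a point or two of power. Both statements are right. They limit the size of the point; they do not argue against using a covariate already in hand.

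Several stronger readings are tempting, and the documents do not support them:

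- **That most women carry anti-AlpN IgG.** SAP 1 says "Most women already have a variety of naturally occurring antibodies against GBS antigens", which concerns GBS antigens in general. Protocol 2.3 says antibodies to the full-length Alp proteins are found in women, without a prevalence. No background AlpN concentration appears anywhere.
- **That the primary comparison is biased.** Randomisation balances baseline in expectation. An additive background would pull the ratio somewhat toward 1 compared with the vaccine-induced part alone (a true 0.60 would appear as 0.62-0.69 for background GMC 0.1-1). But the endpoint is total cord IgG, so that concerns what is measured, not imbalance between groups.
- **That high cut-points are equally exposed.** A regimen at 0% against Group 1 at 5% would pass 82% of the time. However, the phase I rates at 4 µg/mL are 61-91%, and the log-normal fit puts the lowest antigen, Rib, at about 35% above 8 µg/mL. At 0% against 35% the pass probability is essentially nil.
- **That an ineffective schedule could be selected.** Groups 2-4 all receive vaccine, and each is also judged on the GMC ratio and the higher cut-points. A regimen at 95% above 0.1 µg/mL from background alone would have a GMC of about 0.37-1.18, against about 5.3 for Rib on the phase I fit: a ratio of 0.07-0.22, far below 2/3.

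It is also fair that SAP 4.5 reports GMCs and proportions with 95% intervals for every group, placebo included, and confines the tests to descriptive use. That reduces the cut-point issue. It does not replace the between-group placebo estimates that the protocol promised.

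**Conclusion.** The point holds as one of precision. The primary cord-blood GMC ratio omits a pre-treatment covariate that the study collects and uses elsewhere. At log-SD 1.0-1.2 the test has about 72-58% power unadjusted. Adjustment would add roughly 1 to 11 percentage points for r between 0.2 and 0.5. Both SD and r are assumptions, and a simple additive background points to the lower end.

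The low cut-point issue is conditional. It arises only if natural background puts about 93% or more of unvaccinated babies above the cut-point while Group 1 is near 100%. The documents cannot show whether that happens. What they do show is that the SAP dropped the placebo risk differences that would reveal it, without recording the change.

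**What to change.** **SAP 4.5, concentrations.** Estimate the cord-blood GMC ratios, with 90% intervals, from a linear model of log cord IgG on group, the mother's log Visit 1 IgG to the same antigen, and site (as Protocol 7.3 requires) or region as in SAP 4.6, stating which and why. Keep the unadjusted ratio as a sensitivity analysis.

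**SAP 4.5, proportions.** Restore the protocol's risk differences with 90% intervals for Groups 1-4 against Group 5 at every cut-point and antigen. State that non-inferiority at a cut-point is read beside the Group 1 minus placebo difference.

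A hard rule, reading non-inferiority only where the lower bound of that difference exceeds 15 points, is not advised. With 30 placebo babies and true rates of 95.65% and 70%, it would be met only 37% of the time despite a real difference of about 26 points.

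**Cost.** SAP wording and programming only; no new data. The small downside is that a rule must be fixed in advance for mothers without a Visit 1 value. If the placebo risk differences are to stay out, SAP 7 should say so and give the reason.
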